The first objective (**Intervention 1**) will be achieved by comparing whole-body heat storage (measured using combined direct and indirect calorimetry) and the accompanying changes in body temperature (i.e., rectal, mean skin temperature), cardiovascular, and circulating and intracellular inflammatory and stress responses between young and older adults during a 9-hour resting exposure to ~40°C and ~10-15% relative humidity conditions (heat index: 37-38°C). These conditions were chosen to simulate peak temperatures experienced during heatwaves and are similar to conditions in recent heatwaves in North America in 2018 (Ottawa, Ontario; 34°C and 58%, heat index: 41°C) and Europe in 2003 (Paris, France; 38°C and 25%, heat index: 38°C). This intervention will thereby allow for the determination of whether ecologically valid heatwave conditions exceed the physiological capacity for heat dissipation in older adults, and how thermal and cardiovascular strain and inflammation develops during long-duration heat exposure.

The second objective (**Intervention 2**) will be accomplished by comparing physiological responses in the older adults in Intervention 1 to a separate age-matched group removed from the heat to spend 2 hours in a cooler environment (23°C, ~50% relative humidity) approximately mid-way (hours 5-6) through the simulated heatwave. Comparing whole-body heat storage and body temperature, cardiovascular, and inflammatory responses during and after the ambient cooling intervention to the non-cooled group will allow for determination of whether short-term cooling confers prolonged reductions in physiological strain or if the cooling-induced physiological alterations occur only transiently.

Hypotheses

Intervention 1: Age-related attenuation of the human heat loss responses (cutaneous vasodilation and sweating) means that older adults experience greater elevations in body heat storage and body core temperature compared to younger individuals during heat stress. For example, Kenny et al. (*Temperature (Austin)*. 2016 31;4(1):79-88). observed ~80% greater heat storage (equivalent to a ~0.5°C greater elevation in mean body temperature) in middle-aged-to-older compared to young adults during 3-hours of resting heat exposure. More importantly, the middle-aged-to-older adults did not achieve a state of heat balance (i.e., they were still storing heat within their body at the end of the 3 hours).

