Based on this work, our primary hypothesis is that older adults will not achieve a state of heat balance (i.e., rate of heat loss balancing the rate of heat gain; thermal equilibrium) and therefore experience greater heat storage throughout the 9-hour simulated heatwave compared to the younger participants. Consequently, body core temperature will be greater in the older adults and between-group differences will be exacerbated as exposure progresses. We will also explore the secondary hypothesis that differences in body temperature will be paralleled by greater alterations in cardiovascular variables and circulatory and intracellular markers of acute inflammation and stress in the older adults.

Intervention 2: Our primary hypothesis is that body heat storage will be exacerbated in the older adults exposed to the cooling centre intervention upon return to the heat (hours 5-6) compared to the older adults from Intervention 1 who remained in the heat. Consequently, body core temperature will be comparable (statistically equivalent) between groups by the end of exposure (i.e., 9 hours, 3 hours after return to the heat). This is because body temperature is regulated through a negative feedback mechanism. Elevations in core and skin temperatures elicit proportional activation of cutaneous vasodilation and sweating to facilitate heat loss and stabilize body temperature. Thus, core and skin cooling will suppress heat loss and, upon return to a hot environment, heat will be rapidly gained until body temperature rises to an extent sufficient to activate heat loss and re-attain thermal equilibrium. We will also evaluate the secondary hypothesis

that, in parallel to body core temperature, any effect of cooling on cardiovascular responses and acute inflammation will be abated by the end of the heat event.

METHODS

Participants

A total of 20 young (age: 18-30 years) and 40 older (age: 64-80 years) adults will be recruited for the project. Young (n=20) and older (n=20) adults will be recruited for **Intervention 1** and a separate cohort of older adults (n=20) for **Intervention 2**. Details on the determination of the sample sizes for each intervention are provided below.

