2018 (Ottawa, Ontario; 34°C and 58%, heat index: 41°C) and Europe in 2003 (Paris, France; 38°C and 25%, heat index: 38°C). The participant will sit quietly for 3-hours (hours 1-3) within the calorimeter chamber while whole-body heat exchange is measured. Metabolic heat production will be evaluated simultaneously via indirect calorimetry (AMETEK model S-3A/1 and CD 3A, Applied Electrochemistry, Bastrop, TX, USA). At the 3-hour mark, participants will exit the calorimeter, and the brief cardiovascular test battery will be performed again, followed by a measurement of body mass.

Hours 4-6 will be spent resting in the heat in the thermal chamber (but outside of the calorimeter). During this time, the participant will be allowed to consume a light (~300 g), self-provided lunch with low water content (e.g., peanut butter sandwich). Tap water will be available *ad libitum* via a self-service insulated water cooler located in the thermal chamber (out of direct sight). Another cardiovascular battery will be performed followed by a measurement of body mass at the end of this period. The participant will then be transferred to the calorimeter where the final 3 hours will be spent resting in the seated position (hours 6-9). At the 9-hour time point, the participant will be removed from the calorimeter, the cardiovascular test battery was conducted, and a venous blood sample and body mass measurement will be procured. The participant will then be provided with water and/or a commercially available sports drink before leaving the laboratory.

Intervention 2: Efficacy of a cooling centre intervention for limiting physiological strain in the elderly

The protocol for Intervention 2 will be identical to that of Intervention 1 except that after the first calorimeter session and the subsequent cardiovascular battery, the participant will be removed from the thermal chamber to spend 2 hours (hours 5-6) seated in an air-conditioned room (~23°C, ~50% relative humidity). Like protocol 1, the participant will be able to consume water (tap) *ad libitum* and eat a small self-provided during this time. The third cardiovascular battery will be performed in the cooled environment. At the end of the 6th hour, participants will re-enter the calorimeter where they will spend the remaining 3 hours of exposure seated in the heat.

Measurements

Primary Outcome measures

Whole-body heat storage and body core temperature

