a sampling rate of 175 Hz). Normal-to-normal beats, as determined by the Zymed annotation algorithm, will be retained for further analysis. Continuous Individualized Variability Analysis (CIMVA) software (<http://ohridal.org/cimva/CIMVA-CoreDescription.pdf>) will be used to derive absolute heart rate and indices of heart rate variability (5 min windowed analysis with 30 sec time step). The latter includes 1) standard deviation of successive normal-to-normal intervals (SDNN), an index of overall variability; and 2) the root mean squared of the standard deviation (RMSSD) of successive normal-to-normal intervals, which is more reflective of short-term high frequency fluctuations in heart rate (mediated primarily by the parasympathetic nervous system).

Arterial systolic and diastolic blood pressures will be intermittently taken as an average of the three values measured at the brachial artery (~30 s between measures) via manual auscultation. Mean arterial pressure will be calculated as $2/3$ diastolic pressure + $1/3$ systolic pressure. Rate pressure product, an index of myocardial work, will also be derived as heart rate \times systolic pressure.

Brachial arterial blood pressures and cardiac output will be estimated from beat-to-beat recordings of arterial pressure waveform measured at the right middle-finger using the volume-clamp technique (Finometer Pro, Fina-press Medical Systems). Stroke volume will be calculated as cardiac output \div heart rate, whilst total peripheral resistance is derived as mean arterial pressure \div cardiac output. Cardiac baroreflex sensitivity will be determined via the sequence technique using software provided by Finapres Medical Systems (PRVBRS, Fina-press Medical Systems). Forearm and calf blood flows will be determined as the average of a minimum of four measurements obtained via automated venous occlusion plethysmography (Hokanson AI6, D.E. Hokanson, Inc.).

Circulating and intracellular inflammation and stress markers

Venous blood will be collected for the determination of circulating and intracellular inflammation/stress responses. Samples collected from the antecubital vein at baseline and the end of exposure will be transferred directly into Vacutainer tubes with no additive (1 x 5 mL SST™ Serum Separator Tube, BD) or potassium ethylenediaminetetraacetic acid (1 x 3 mL and 3 x 10 mL K₂EDTA [7.2 mg and 18 mg, respectively], BD).

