Statistical analysis for **Intervention 1** will compare whole-body heat storage and the resultant progression of body temperature, cardiovascular and acute inflammatory responses between the young and older adults during the simulated heatwave. Whole-body heat storage (primary outcome), body temperature responses including rectal temperature (primary outcome) and mean skin temperature (secondary outcome), as well as cardiovascular responses (secondary outcomes) will be evaluated using linear mixed-effects models. Time will be modelled as a repeated within-subject fixed effect (two levels: 3 and 9 hours), and age-group (two levels: young and older adults) will be modelled as a between-subject fixed effect. Pre-heat exposure values of the outcome variable, participant sex, and self-reported weekly physical activity (min/week, as assessed via the GAQ) will be included as covariates. Circulating and intracellular markers of acute inflammation and stress (secondary outcomes) will be evaluated using a similar model but without the fixed effect of time (data was only collected at the end of exposure) and baseline values included as a covariate (where appropriate). Participant identification will be modeled as a random effect in all analyses. Akaike's information criterion will be used to determine random effect and variance/covariance structures.

Post hoc multiple comparisons will be made on model estimated marginal means. Given the small number of comparisons for each variable, multiplicity corrections will not be employed. Homoscedasticity will be evaluated for all models by visual assessment of residual plots. Approximate normal distribution of residuals will be assessed via visual inspection of histograms and Q-Q plots. Data will be log-transformed in the event that the distribution of residuals meaningfully deviates from normality. For all analyses, the level of significance will be set at $P < 0.050$. Descriptive statistics will be presented as means and standard deviations. Comparisons between groups and/or time-points will be presented as means and 95% confidence intervals [lower limit, upper limit].

Intervention 2

Statistical analysis for Intervention 2 will evaluate the acute and lasting impacts of the short-term cooling intervention (i.e., during cooling and following return to the heat, respectively) on physiological responses.

Cumulative heat storage (primary outcome)

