corresponds to an equivalence of means. These are presented alongside the results of a traditional Welch's t-test. This permits evaluation of both statistical differences, and statistical equivalencies in physiological responses. Performing analysis on the marginal means will allow for isolation of the effect of cooling from individual differences in the body temperature response to heat exposure (captured in the 3-hour timepoint covariate). Equivalence bounds will be set to $\pm 0.3^{\circ}\text{C}$, which corresponds to the typical day-to-day variation of core temperature (Consolazio et al. *Physiological measurements of metabolic functions in man*. 1963:453-480) and has been suggested to reflect a meaningful/detectable change in body temperatures in a recent study assessing the influence of cooling strategies on physiological strain in young adults (Morris et al. *Annals of Internal Medicine*. 2019;171(9):675-677).

Secondary outcomes

Mean skin temperature as well as cardiovascular responses and circulating/intracellular inflammatory/stress markers will be modeled with linear mixed-effects models. The analyses for mean skin temperature and cardiovascular responses will be performed similar to that for rectal temperature except only two time points will be included (0- and 3-hours post-cooling intervention). Circulating and intracellular changes in inflammatory markers, measured at the start and end of exposure only, will be analyzed with a linear mixed-effects model with age-group (two levels: young and older adults) modelled as a between-subject fixed effect, and participant sex, self-reported and weekly physical activity (min/week, as assessed via the GAQ), included as covariates.

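### Inflammation and stress markers are sampled only at baseline and hour 9, so the stated aims of showing how inflammation develops and whether a cooling effect on it is prolonged or transient cannot be met for these outcomes

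*Combined protocol and SAP*

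**What the plan says.** **Sampling.** Under Circulating and intracellular inflammation and stress markers, blood is taken as "Samples collected from the antecubital vein at baseline and the end of exposure". The Statistical analysis plan agrees. For Intervention 1 the marker model has no time effect because "data was only collected at the end of exposure", with baseline as a covariate where appropriate. For Intervention 2 (Secondary outcomes) the markers are described as "measured at the start and end of exposure only".

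**Aims.** Research Project Objectives says Intervention 1 will show "how thermal and cardiovascular strain and inflammation develops during long-duration heat exposure". For Intervention 2 it lists inflammatory responses among those to be compared between groups both during and after cooling. That comparison is to decide between two readings: a prolonged reduction in strain, or alterations that are only transient. Under Hypotheses, the secondary hypothesis for Intervention 2 is that "any effect of cooling on cardiovascular responses and acute inflammation will be abated by the end of the heat event".

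**Analysis.** The introduction to the Intervention 2 analysis says it will "evaluate the acute and lasting impacts of the short-term cooling intervention (i.e., during cooling and following return to the heat, respectively"). The later text on secondary outcomes is narrower. It focuses on whether an effect remains 3 hours after return to the heat, and it labels the equivalence tests exploratory.

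**The concern.** A claim that inflammation develops in a certain way, or that a cooling effect on it was transient, needs at least one measurement between the start and the end. For the markers there is none. The objectives offer prolonged and transient as the two possible readings and leave out a third, that cooling never changed the marker. Read literally, a null marker comparison at hour 9 falls under transient by default. The report could then say that cooling centres bring a short-lived anti-inflammatory benefit that nobody measured, in a study meant to inform advice on visiting cooled locations.

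**Working it through.** **1. What is measured when** (Experimental Design and Measurements)

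| Time | Rectal and skin temperature | Cardiovascular battery | Marker blood |
|---|---|---|---|
| Baseline | yes | yes | yes |
| Hour 3 (before cooling) | yes | yes | none listed |
| Hour 6 (end of cooling) | yes | yes | none listed |
| Hour 9 | yes | yes | yes |

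At hour 3, "the brief cardiovascular test battery will be performed again, followed by a measurement of body mass". At hour 6, "Another cardiovascular battery will be performed followed by a measurement of body mass at the end of this period"; in Intervention 2 this battery is done in the cooled room. Could blood sampling be part of the battery? The procedures suggest not: at baseline and at hour 9 the venous sample is listed separately from the battery, and the two marker passages in the analysis plan confirm two draws only.

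The markers are serum TNF-α, IL-6 and CRP (3) and intracellular HSP70, HSP90, TNF-α and IL-6 (4), so 3 + 4 = 7 outcomes, each with 0 intermediate samples.

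**2. What the hour-9 data can separate**

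Let D(t) be the cooled minus non-cooled difference at hour t. Only D(9) is observed after baseline.

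- Cooling never acted: D(6) = 0 and D(9) = 0.
- Cooling acted and the effect wore off: D(6) ≠ 0 and D(9) = 0.

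Both give the same distribution at hour 9, so no test, covariate or sample size tells them apart. A non-zero D(9) would show a difference at the end but not when it arose. In Intervention 1, two samples likewise give one net change per person and no course.

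**3. How easily a null would arise**

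This step shows only that the ambiguous result is a likely one.

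*The plan's own figure.* For equivalence within 1 SD, true difference zero, 0.05 per side and 80% power, n = 2[(z(0.95) + z(0.90))/1.0]² = 2(1.645 + 1.282)² = 17.1, so 18 per group. This matches the stated 18. Exact t-based power is 77.3% at 17 and 80.5% at 18.

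*Inputs for the markers.* 20 per group (Participants); two-sided 0.05 for the difference test; a bound of 1 SD for outcomes without a named bound, read as the standardised bound of 1.0 used in the sample size section. Covariate gains are ignored, and the residual effects d are assumptions. The noncentrality is d√(20/2) = 3.16d on 38 degrees of freedom.

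| True hour-9 difference (SD) | Difference test non-significant | Declared equivalent within 1 SD |
|---|---|---|
| 0 | 95% | 86% |
| 0.3 | 85% | not computed |
| 0.5 | 66% | 46% |
| 0.8 | 31% | not computed |

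An 80% chance of detecting a difference needs d of about 0.91. A null is therefore probable if nothing remains at hour 9, and quite possible if a moderate effect does remain. In neither case does it show that an earlier effect disappeared.

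**The case against.** The strongest reply is that the operative analysis text is already narrow. The secondary-outcome analysis asks whether an effect remains 3 hours after return to the heat, and an hour-9 sample can address that. This stands, and the hour-9 comparison is worth keeping.

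Four stronger readings are tempting, and the documents do not support them.

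- *The plan will report a null as a transient effect.* No section contains such a reporting or decision rule; the wording only invites it.
- *The hypothesis asserts that cooling did change inflammation.* It speaks of any effect, which is conditional, and hour-9 data can contradict it. But it would also be satisfied if cooling had done nothing, so it cannot support a claim about an effect that came and went.
- *An acute marker analysis has to be removed from the analysis plan.* The sentence on acute and lasting impacts is a general introduction. The outcome-specific text gives the markers no during-cooling analysis.
- *The Intervention 1 hypothesis needs a matched time course.* Its statement that temperature differences will be paralleled by larger alterations in older adults can mean larger net changes alongside larger temperature differences, which a baseline-adjusted hour-9 comparison addresses.

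It is also fair that two draws may be a reasonable practical choice and that the markers are secondary. What remains is that the objectives claim a time course and a during-cooling comparison for inflammation, and nothing later in the document withdraws them.

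**Conclusion.** The point holds as a mismatch between stated aims and sampling. For all seven markers the effect of cooling during or just after the cooling period is not estimable at any sample size, and neither is the course of inflammation in either intervention. Net change to hour 9 and the hour-9 group difference are estimable. Whole-body heat storage, rectal temperature, skin temperature and the cardiovascular outcomes are outside this gap.

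The conclusion rests only on the sampling schedule, on which the procedures and the analysis plan agree. The percentages in the working depend on the assumed residual effects and on ignoring covariates; the conclusion does not depend on them. The point is worth correcting because the remedy is cheap and the unsupported conclusion would concern a public health recommendation, but it does not threaten the primary results.

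**What to change.** No added blood draws are proposed. The plan states that it was submitted after the full data set had been cleaned and analysed, though before unblinding, so the changes should be recorded as a dated clarification.

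1. **Research Project Objectives.** For inflammation, replace the claim about how it develops with net change from baseline to hour 9. Take inflammation out of the during-cooling comparison and out of the prolonged-versus-transient determination.
2. **Hypotheses, Intervention 2.** Restrict the marker hypothesis to the hour-9 difference between cooled and non-cooled groups, adjusted for baseline and reported as an estimate with its confidence interval. Do not word it as an expectation of no difference: a true difference of 0.5 SD would be non-significant about 66% of the time.
3. **Statistical analysis plan, Intervention 2, Secondary outcomes.** State that a null or equivalent marker result at hour 9 cannot separate no effect from a transient one, and will not be reported as an abated or transient effect of cooling.

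A related matter in the same section: the Intervention 2 marker model names age-group (young and older) as its between-subject factor. The comparison in item 2 needs cooling versus no cooling there.

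The cost is a narrower secondary claim. Items 1 to 3 change no sample size, blood draw or primary analysis.

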Non-additive blood will be let to sit for 20 min to clot before centrifugation at 1.38 relative centrifugal force (RCF) for 10 min (room temperature). Separated serum will then be transferred into polypropylene Eppendorf tubes, and frozen and stored at -80°C. Serum concentrations of tumor necrosis factor alpha (TNF- α , DY210-05, Bio-Techne), interleukin-6 (IL-6, DY206-05, Bio-Techne) and C-reactive protein (CRP, DY1707, Bio-Techne) will be analysed via an enzyme-linked immunosorbent assay (ELISA) kits with provided ancillary reagents (DuoSet ELISA Ancillary Reagent Kit 2, DY008, Bio-Techne) according to the manufacturer's protocol. A 1:2 sample to reagent diluent ratio will be used, and plates will be read on a plate reader at a wavelength of 450 nm (Synergy, Biotek). Circulating protein concentrations will be corrected for the change in plasma volume during heat exposure (described below).

Whole blood (from K₂EDTA tubes) will be immediately layered on histopaque (Histopaque-1077, Sigma-Aldrich) and centrifuged at 0.8 RCF for 30 min (22°C). The peripheral blood mononuclear cell (PBMC) layer will then be separated and washed with phosphate buffered saline (P4417, Sigma-Aldrich) and centrifuged again at 1.1 RCF for 10 min (4°C). Isolated PBMCs will be resuspended in phosphate buffered saline, transferred to 1.5 mL microcentrifuge tubes, and centrifuged a final time at 9.8 RCF for 10 min (4°C). Any remaining supernatant will be aspirated prior to storing the PBMC pellet at -80°C until analysis.

For analysis, the PBMC pellet will be lysed on ice for 30 min in a lysis buffer consisting of Tris-HCL 8.0 pH (15568-025, Invitrogen, Thermo Fisher Scientific), 0.5M EDTA (15575-020, Invitrogen, Thermo Fisher Scientific), 1.5M NaCl (S3014, Sigma-Aldrich), 1% Triton X 100 (X100, Sigma-Aldrich), and freshly added protease (78430, Thermo Fisher Scientific) and phosphatase (7842, Thermo Fisher Scientific) inhibitors. The lysate is then quantified (DC-protein assay, 5000112, Bio-Rad) and normalized to a total protein concentration of 40 μ g, which was then electrophoresed on 12% polyacrylamide SDS-PAGE gels.

The proteins are then electrotransferred to nitrocellulose membranes (162-0112, Bio-Rad) then blocked in tris buffered saline (TBST) (150 mM NaCl, pH 8.0) containing 0.2% polysorbate detergent (Tween 20; 170-6531 Bio-Rad) and 5% powdered milk (170-6404,

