Bio-Rad) for 60 min at 4°C with gentle agitation. After blocking, nitrocellulose membranes will be incubated at 4°C over-night with primary antibodies (HSP70-inducible form 1:1000, no. 4876S, Cell Signaling Technology; HSP90, Cell Signaling Technology, no. 4875S; TNF- α P300A Invitrogen, Thermo Fisher Scientific; IL-6, PA1-26811, Invitrogen, Thermo Fisher Scientific; β -actin HRP conjugate 1:10000, no. 12262S, Cell Signaling Technology). Following primary antibody incubation, the membranes will be washed repeatedly (3 times, 10 min each) in TBST and incubated with an HRP-conjugated secondary antibody (Anti-rabbit IgG, HRP-linked, no. 7074, Cell Signaling Technology) at room temperature for 1 hour and then washed again 3 times in TBST (10 min per wash). The nitrocellulose membranes will be visualized using the Clarity Max Western ECL Blotting substrate (1705062, Bio-Rad) and C-Digit Blot Scanner (LI-COR). Membranes will be stripped and re-probed with Restore Western Blot Stripping Buffer according to the manufacturer instructions (no. 21063, Thermo Fisher Scientific). Protein bands will be quantified by Image Studio Digits software (LI-COR, version 5.2) and normalized to β -actin, which served as an internal control.

Hydration-related variables

Baseline (start of session) urine specific gravity will be assessed with a hand-held total-solids refractometer. (Reichert TS 400 total solids refractometer, Reichert). Participants presenting to the laboratory with urine specific gravity <1.025 will be considered adequately hydrated to begin the experimental session (Kenefick & Cheuvront. Hydration. *Nutr Rev.* 2012;70 Suppl 2:S137-142). Throughout each intervention, fluid status was monitored via changes in body mass using a high-performance digital weighing terminal (model CBU150X, Mettler Toledo Inc).

Additional whole blood (not used in PMBC extraction) will be used to measure haematological parameters in duplicate (Ac-T diff, Beckman Coulter). Haemoglobin and haematocrit will be used to estimate changes in plasma volume from the start to end of the 9-hour exposure (Dill & Costill. *J Appl Physiol.* 1974;37(2):247-248).

Statistical analysis plan

Intervention 1

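### The Western-blot markers need several membranes, but the plan gives no layout, common reference sample or membrane term, so membrane variation can enter the group contrasts

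*Combined protocol and SAP*

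**What the plan says.** - **Numbers (Participants).** "A total of 20 young (age: 18-30 years) and 40 older (age: 64-80 years) adults will be recruited". The 20 cooled older adults are a separate cohort from the 20 older adults of Intervention 1.
- **Samples (Circulating and intracellular inflammation and stress markers).** "Samples collected from the antecubital vein at baseline and the end of exposure" supply the assays. Cells are isolated and frozen, the last step being "storing the PBMC pellet at -80°C until analysis".
- **Blots (same section).** Lysate is set to 40 μg protein, "which was then electrophoresed on 12% polyacrylamide SDS-PAGE gels". HSP70, HSP90, TNF-α and IL-6 are probed. "Membranes will be stripped and re-probed with Restore Western Blot Stripping Buffer". Bands are divided by β-actin, "which served as an internal control".
- **Intervention 1 marker model (Statistical analysis plan).** Age group, sex and weekly activity, with baseline as a covariate only where appropriate.
- **Intervention 2 marker model (Secondary outcomes).** The markers, "measured at the start and end of exposure only, will be analyzed with a linear mixed-effects model". The listed covariates are sex and activity, with no baseline value. The subject of that sentence is changes in the markers, so it is unclear whether the outcome is the change or the end value. The group factor is named as age group, although the comparison is cooling against no cooling.
- **Random effects (both interventions).** Participant is the only one named. Akaike's criterion chooses the structure, and no membrane, gel, plate or batch candidate is listed.

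The document gives no gel count, no allocation of participants or time points to membranes, and no inter-membrane calibrator.

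**The concern.** A β-actin ratio corrects for how much protein went into a lane. It may also cancel part of any membrane effect that acts equally on both signals. It cannot cancel effects specific to one antibody, one exposure or one strip-and-reprobe round, so ratios from different membranes are not guaranteed to share a scale.

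Both planned contrasts (young against older, cooled against not cooled) are between participants and so cross membranes. With one end value per person, a participant intercept cannot be separated from the residual, so it does not absorb variation shared by everyone on a membrane.

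At stake are the secondary claims on intracellular stress and inflammation proteins in both interventions. The cooled cohort deserves most attention. It is recruited separately, so assay in order of collection would put it on its own membranes, and its model lists no baseline covariate.

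**Working it through.** The plan gives no power or error figure for the blot markers, so there is nothing to reproduce. The check asks how many membranes are needed and what they do to the error rate under different layouts.

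**Step 1: number of membranes.** (20 + 40) × 2 = 120 lysates. At an assumed 15 or 10 lanes, 120/15 = 8 or 120/10 = 12 gels. Several membranes are unavoidable.

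**Step 2: mechanism when membranes track group.** Inputs: 20 per group (document); 4 membranes per group with 5 participants each, i.e. 10 sample lanes (assumption); person SD s and membrane SD m on the log scale (assumptions).
- True variance of the group difference: 2(m²/4 + s²/20).
- Average variance the model reports without a membrane term: 2(s² + m²·15/19)/20.
- Example, s = 0.4 and m = 0.2: true 2(0.010 + 0.008) = 0.0360; reported 2(0.160 + 0.0316)/20 = 0.0192. The standard error is too small by a factor √(0.0360/0.0192) = 1.37.
- The critical value 2.02 then acts like 2.02/1.37 = 1.48, a two-sided error of about 14%.

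**Step 3: simulation.** 20 against 20, no true effect, two-sided 5% level, 20,000 runs per cell, s = 0.4–0.5, assumed baseline–end correlation 0.5, both samples of a person on one membrane. The sex and activity covariates were left out.

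| Layout and analysis, no membrane term | m = 0.1 | m = 0.2 | m = 0.3 |
|---|---|---|---|
| Membranes track group, end value | 7–8% | 12–15% | 18–22% |
| Membranes track group, same-membrane baseline covariate | 6% | 7–8% | 8–9% |
| Membranes track group, log change score | 5% | 5% | 5% |
| Random allocation, end value | 5% | 5% | 5% |
| Balanced (2 + 2 participants per membrane), end value | 4–5% | 3–4% | 2–3% |

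The baseline covariate does not remove everything because its fitted slope is below 1. The change score does, because a shared additive effect cancels.

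**Step 4: other assumptions.** A second simulation (3,000 runs per cell) set the membrane share of variance at 10–50%.
- One group per membrane, end value: 9–23% with 4 participants per membrane, 11–31% with 6.
- An 80/20 mix of groups: 6–15%.
- A baseline value on a different membrane from the end value gives no protection: 10–34% with one group per membrane.

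**Step 5: power in a balanced layout.** For an assumed true effect of 0.9 person SDs, power without the term is 77–78%, 72–75% and 64–69% at m = 0.1, 0.2 and 0.3. With a membrane effect fitted it stays at 78–79%.

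**Step 6: can a model term rescue full nesting?** A fixed membrane effect is then aliased with group. Testing on membrane means, which is what a random intercept amounts to in an equal-sized layout, restores about 5% error. With 4 membranes per group, however, power for an assumed effect of 1.06 person SDs is 62% falling to 21% as the membrane share rises from 10% to 50%. With no membrane variation, 20 per group would give 90%.

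**The case against.** The strongest reply is that the document is silent on layout, and silence is not evidence of a bad one. A reader might infer that batch does produce false age or cooling effects, or that no reference lysate is loaded. Neither is established. Pellets are frozen for later assay, so all groups could have been run together, and a balanced or random layout gives no inflation. This stands: the inflated rates are conditional on membranes tracking group.

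Second, the planned models may already protect the contrast. Intervention 1 allows a baseline covariate, and the Intervention 2 wording can be read as analysing change. This stands in part. Either device works only if both samples of a person share a membrane, which is not stated. The Intervention 1 covariate is optional, and the Intervention 2 outcome is ambiguous.

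Third, the closing paragraph on Intervention 2 says the analysis plan was submitted after the full data set had been cleaned and analysed, though before unblinding. If that includes the blots, layout advice comes too late. This also stands and shapes the fix.

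A reader might extend the argument to the ELISA markers with one plate per group. That needs duplicate serum wells and a particular number of standard wells, neither of which the document gives, and plate standards remove part of any plate effect. The blot error rates should not be carried over.

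**Conclusion.** The gap is real but conditional. Several membranes are needed, β-actin is the only stated normalisation, and no model term represents membrane. If membranes track group, type I error on end values would be roughly 7–22% instead of 5%. A same-membrane baseline covariate lowers this to about 6–9%, and a log change score returns it to 5%. Balanced layouts cost power, not validity. Random layouts hold about 5% on average over allocations.

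All membrane and person SDs, lane counts and the baseline–end correlation are assumptions; the document supplies none. Only secondary outcomes are affected, and the heat-storage and rectal-temperature conclusions are untouched. The change is worth making because it is cheap and the secondary hypotheses in both interventions make claims about these proteins.

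**What to change.** **In the analysis plan, whatever the state of the assays:**
- Add membrane as a random intercept in the blot marker models. Keep it as a design term that Akaike's criterion cannot drop, and use Kenward–Roger or Satterthwaite degrees of freedom.
- In the Intervention 2 marker model, include the baseline value from the same membrane, state whether the outcome is the end value or the change, and name cooling group as the factor.

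**If the assays have not been run:**
- Put both samples of a participant on one membrane.
- Balance the compared groups over membranes.
- Load one pooled reference lysate on each membrane and scale the ratios to it.
- Balancing groups over ELISA plates is sensible on the same grounds.

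**If they have been run:**
- Report which samples shared membranes.
- Fit the term where groups share membranes.
- Where membrane and group are fully confounded, say so as a limitation. The term cannot recover the lost information.

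**Cost.** No new participants or procedures: a layout sheet, one lane per gel, some extra analysis, and assays held until all groups are collected. Strict balance over all three groups uses more gels. One participant from each group takes 3 × 2 = 6 lanes plus 1 reference, so 20 gels of 10 lanes. Two from each take 12 + 1 = 13 lanes, so 10 gels of 15 lanes. The minimum counts are 12 and 8. Approximate balance, with the compared groups present on every membrane, reduces that cost.
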